## 1. Abstract

Smoking is the leading preventable cause of morbidity and mortality in Maryland. Smokers are at increased risk of many cancers, heart disease and chronic obstructive pulmonary disease. Quitting smoking reduces the risk of these life-threatening conditions. In Maryland, annual expenditure on the treatment of cancer and smoking related diseases is approximately \$3.5 billion. Therefore, continued prioritization of smoking cessation services is necessary to reduce the health and economic burden of smoking-related diseases.

While smoking cessation services such as nicotine replacement therapy and counseling are available, they are expensive and not easily accessible to everyone. Real-time biological feedback in clinic settings and mobile phone-based cessation support both independently show evidence of increasing a smoker's likelihood of quitting. The combination of these two strategies into a tailored system for smoking cessation is highly innovative and has the potential to provide an effective, inexpensive, and widely accessible tool for smokers attempting to quit. With smartphone use so widely prevalent, an interactive biofeedback and text message-based cessation program has great potential to decrease the heavy burden of tobacco use. We are currently working with partners to develop COach2Quit, a novel smartphone application that links to an individualized carbon monoxide (iCO) monitor and integrates biomarker feedback with appropriate motivational messaging.

The objective of this proposal is to conduct a randomized controlled trial to determine whether the use of the COach2Quit application reduces smoking more than brief advice for smoking cessation. We hypothesize that real time biomarker feedback and messaging support from the COach2Quit app will lead to greater smoking cessation rates than brief anti-smoking advice alone. If effective, the COach2Quit app could be an easily accessible and cost-effective tool to help smokers quit. The findings from this trial could have implications for the delivery of future outpatient smoking cessation programs.

## 2. Objectives (include all primary and secondary objectives)

1. To assess the efficacy of the COach2Quit smoking cessation application by comparing smoking cessation rates at 2-weeks and 1-month among participants using the COach2Quit app and participants receiving brief anti-smoking advice (primary outcome is 1- month). *We hypothesize that the 1-month quit rate will be 20% in the COach2Quit arm and 10% in the brief anti-smoking advice arm.*

2. To evaluate whether the treatments differentially influence cognitive and behavioral processes related to cessation outcomes. Although formal mediational analysis is precluded by the moderate sample size in this pilot investigation, we will examine how treatments affect various intermediate variables assessed during and at the end of treatment including; (1) Urges to smoke; (2) Withdrawal symptoms; (3) Reinforcing Smoking Decisional Balance; (4) Smoking Abstinence Self-Efficacy; and, (5) Satisfaction with the program. *We hypothesize these measures will all benefit with COach2Quit compared to brief advice alone.*

## 3. Background (briefly describe pre-clinical and clinical data, current experience with procedures, drug or device, and any other relevant information to justify the research)

Tobacco is the leading cause of death in the world, contributing to 6 million deaths each year; nearly 500,000 of these deaths occur in the US with an additional 50,000 deaths due to exposure to second hand smoke. Most recent estimates state that 19% of US adults smoke; although Maryland is under the

Dated: 15 May 2017

national average at 16%, the prevalence in Baltimore City is 21%. Smokers are at increased risk of many cancers, heart disease and chronic obstructive pulmonary disease. Quitting smoking reduces risk of these life-threatening conditions.

In Maryland, approximately 149,600 residents are afflicted with at least one smoking induced chronic disease and smoking is responsible for 7,490 deaths each year on average. Tobacco use is responsible for more deaths than homicide, suicide, HIV/AIDS and accidental injuries and overdoses collectively. The economic burden of smoking is also high, with an annual expenditure of \$3.5 billion going towards the treatment of cancer and smoking-related diseases. Therefore, continued prioritization of smoking cessation services is necessary to reduce the health and economic burden of smoking-related diseases.

### **Carbon Monoxide (CO) monitoring for smoking cessation**

CO in exhaled breath is a commonly used tool for measuring adherence to smoking cessation. Exhaled CO (eCO) has also been considered as a cessation tool in primary care, however it has not been thoroughly studied. Current evidence is only available for clinic-based use of eCO and suggests that cessation increases significantly following measurement, though the impact is short lived. Pilot studies indicate that **more frequent and personal use of eCO may be an effective cessation tool.** Beard and West report declining cigarette consumption after provision of a personal CO monitor over a 6-week period.

Smartphone ownership has been steadily increasing and 64% of adults in America now own a smartphone. This can be leveraged as an interactive modality through which smoking cessation interventions can be delivered. A smartphone application that combines biomarker feedback with message-based support offers the benefits of portability, accessibility and ease of use. There are several existing smoking cessation smartphone applications, but there have been no published studies to date that evaluate their impact on smoking cessation and this has been cited as an area that merits investigation. **Combining brief cessation advice and relapse prevention strategies with daily personal CO monitoring may lead to increases in cessation and prolonged abstinence without the need for pharmaceutical interventions or nicotine replacement therapy.**

## **4. Study Procedures**

### **a. Study design**

**Overview:** The goal of this randomized controlled trial is to assess the efficacy of the novel COach2Quit smartphone application by determining whether the use of this app reduces smoking more than brief anti-smoking advice alone. This will be a two-arm individually randomized trial and participants who are currently smoking will be assigned 1:1 to either study arm. Smoking behavior will be measured through self-report at baseline, 2-week and 1-month follow up visits. Smoking behavior will also be verified by 2 biomarker measurements: carbon monoxide breath test and urine cotinine, collected at baseline, 2-week and 1-month follow-up visits. In addition, participants will receive weekly follow-up calls. **The primary outcome will be smoking cessation at the 1-month follow-up visit.**

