### **Initial Assessment**

After obtaining informed consent, an initial assessment will be conducted with participants. Participants will be asked to provide a baseline CO breath test and a urine sample to ascertain smoking status. If a candidate is deemed ineligible or chooses not to participate, they will be provided with information from the American Lung Association and referred to the Maryland Quit Line. Eligible participants will complete the baseline questionnaire which will include sociodemographic information, aspects of smoking history (e.g., years, quit attempts, etc), smoking urges, withdrawal symptoms and reinforcing effects of smoking, confidence to quit smoking, reasons to continue to smoke (pros) and barriers to quitting (cons), and perceived vulnerability to smoking-related illnesses, as well as other domains. A certified smoking cessation interventionist (SCI) will deliver standardized smoking cessation counseling using the National Cancer Institute's 5A's model (described below in section e). After brief counseling, all participants will set a quit date within the next 2 weeks and receive their randomized group assignment.

Participants in the COach2Quit arm will be provided with an individualized carbon monoxide (iCO) monitor along with instructions on the use of the monitor and the COach2Quit application. The SCI will help the participant install the COach2Quit app on their phone, guide them through completing an initial CO breath test using their iCO monitor connected to their smartphone, and answer any questions they may have. Participants will be requested to use their iCO monitor at least twice per day and answer a few questions about the amount smoked that day. The participant will be informed that their results will be sent to the study team through the application each time the participant uses their iCO monitor.

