## **6. Drugs/ Substances/ Devices**

### **COach2Quit smartphone application and iCO monitor**

Participants assigned to the COach2Quit arm will receive behavioral counseling (described above) and will download the COach2Quit app on their phone. They will be given an individualized carbon monoxide (iCO) monitor and instructed on how to use it with the COach2Quit app. Participants will receive 2 messages daily (1 in the morning and 1 in the evening) requesting them to use the iCO monitor. The iCO monitor has been developed by CoVita™ Bedfont®, and has been made available for the COach2Quit application. The iCO is a personal CO tester that connects to a smartphone via the headphone jack and provides an exhaled carbon monoxide (eCO) reading. Programmers have used the communication protocol supplied by coVita™ Bedfont® to read in data from the iCO monitor and integrate eCO readings with basic feedback messages. The data will be sent to a central data center, with a response message dependent upon CO result. **A measurement of  $\leq 10$  parts per million (ppm) will be a negative result** and will be followed with a message praising the participant's progress. If a positive result is read ( $>10$  ppm), a message of encouragement will follow, along with questions to be answered so that the result can be better understood and acted upon. Subsequent messages will be based on how the user's current CO reading compares to their previous reading. CO trends will be measured over time and the participant will be able to see a graphical display of their CO levels from initiation in to the study. Encouraging responses will also be received when declines in eCO are observed compared to prior results even if above the 10-ppm threshold. Users of the app will also have the option to request a call from a counselor.

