### **Carbon Monoxide Breath Test**

When a smoker smokes a cigarette, or any tobacco product, he/she breathes in carbon monoxide, which competes with oxygen to combine with hemoglobin. Hemoglobin has a 200-250 times greater affinity for CO than for oxygen, thus greatly interfering with the necessary binding of oxygen to hemoglobin. Several machines are available to measure the COHb level in the blood of smokers, providing a means of measuring recent exposure to cigarette smoking. For our study, a point of care test for measuring carbon monoxide will be conducted via the piCO Smokerlyzer from OPS Medical, designed specifically for smoking cessation programs and tobacco control programs. Carbon monoxide will be measured in an exhaled breath in parts-per-million (ppm). **A reading of  $\leq 10$  ppm will indicate abstinence.** Participants will be asked about their smoking history since their last visit and on the day of the CO test. If the participant has a positive CO test, they will be further counseled for smoking cessation if enrolled in the clinical trial. If not in the clinical trial, they will be provided with information from the American Lung Association and referred to the Maryland Quit Line. Results will be recorded and labeled with the participant's study ID, and the participant will see their results immediately and the results will be explained to them.

Dated: 15 May 2017

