### **Urine Cotinine Test**

When a smoker smokes a cigarette or uses nicotine replacement therapy, his/her urine will have detectable levels of cotinine, a nicotine breakdown product. Cotinine is found in urine from 2 to 4 days after tobacco use, providing a means of measuring recent exposure to cigarette smoking. For our study, a point of care test for measuring cotinine levels will be conducted via SmokeScreen®, a rapid colorimetric assay from GFC Diagnostics Ltd. Cotinine levels will be semi-quantified according to the color chart included with the tests. A color change to red/orange indicates a positive sample, with a darker color indicating greater nicotine intake. If the participant has a positive urine cotinine test, they will be further counseled for smoking cessation if enrolled in the clinical trial. If not in the clinical trial, they will be provided with information from the American Lung Association and referred to the Maryland Quit Line. Results will be recorded and labeled with the participant's study ID, and the participant will see their results immediately and the results will be explained to them.

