### **c. Statistical plan including sample size justification and interim data analysis.**

#### **Data analysis plan**

**Overview** The primary outcome measure for the RCT is proportion of participants with biochemically verified smoking cessation as of 1-month; the primary exposure is study arm, brief-advice only vs. COach2Quit. We will compare proportions of smoking abstinence between study arms at 1-month.

Covariates of interest (e.g. sex, age, race, ethnicity, education, income, smoking history) will be assessed for relationship to prevalence of quitting. These comparisons will utilize the chi-square test for categorical variables and either the Student's t-test or the Wilcoxon signed rank test for continuous variables. Multivariate logistic models will be generated using forwards stepwise model selection, including study arm and all variables with  $p < 0.2$  or odds ratio  $< 0.5$  or  $> 2.0$  at the univariate level, ultimately generating the most parsimonious model.

We will conduct intent-to-treat analyses, providing the purest analysis for an RCT. For these analyses, participants who are lost to follow-up will be considered smokers from the date of last contact. This approach is conservative, as it will likely include participants who have not received either study intervention, but point estimates will be biased towards the null. This approach has been widely adopted in smoking cessation studies. We will compare rates of losses to follow up across the study arms, and look for differences in characteristics of those lost between the arms.

We will analyze number of smoke-free days obtained from questionnaires by comparing the proportions of smoke-free days between arms with a Wilcoxon signed rank test. We will estimate either the absolute difference in proportions, or after a  $\log(\text{days smoke-free}+1/\text{total days of follow up})$  transform if appropriate, with 95% confidence intervals. We will also measure durability of treatment effects using consecutive visits with biochemically verified smoking cessation.

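### Breath CO at 10 ppm is both the app's daily feedback signal and a test of quitting; no rule also requires a negative cotinine, so any excess false passes would favour the app.

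*Combined protocol and SAP*

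**What the plan says.** The primary outcome in section 7c is the "proportion of participants with biochemically verified smoking cessation as of 1-month". Section 4a names the verifying tests: "Smoking behavior will also be verified by 2 biomarker measurements: carbon monoxide breath test and urine cotinine".

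CO has two roles in the plan.

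- **As treatment, app arm only.** Initial Assessment (section 4a): "Participants will be requested to use their iCO monitor at least twice per day". Section 6, on the app and monitor, says that a reading at or below 10 "parts per million (ppm) will be a negative result" and is answered with praise. It adds that "the participant will be able to see a graphical display of their CO levels from initiation in to the study".
- **As outcome, both arms.** Section 6, Carbon Monoxide Breath Test, says that a clinic reading at or below 10 "ppm will indicate abstinence". Of every participant, controls included, it says that "the participant will see their results immediately and the results will be explained to them".

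Urine cotinine is not part of the app's feedback. Section 6 gives it a longer look-back: "Cotinine is found in urine from 2 to 4 days after tobacco use".

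The two tests are combined in one place only, the baseline exclusion in section 5, which removes people who are negative on both. No section says which result, or which combination, verifies a quit at 1 month, or how self-report enters.

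**The concern.** The intervention gives one arm repeated practice on a test that also measures the outcome, with the same analyte and the same threshold. A continuing smoker with a monitor can watch how the reading moves with smoking and with gaps between cigarettes, and can check it before a visit. Counting dropouts as smokers does not correct this, because the people concerned attend.

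If the CO test passes more continuing smokers in the app arm than in the control arm, the error is differential and inflates the app's apparent effect. That matters in a pilot whose stated product is estimates for larger trials, because a later sample size would rest on the inflated difference.

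The choice of combining rule is therefore more than a matter of completeness. A sponsor could fill the gap with CO alone, or with either test negative, and build the bias in.

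**Working it through.** **Inputs from the documents.** 150 participants randomized 1:1, so 75 per arm; expected 1-month quit rates 20% (app) and 10% (control) (section 7c, Sample Size). The sample size has no power derivation to reproduce. The reference figure is the hypothesised difference, 20 − 10 = 10 points.

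**Exposure to CO feedback before the 1-month test.**

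- App arm: 2 readings × 28 to 30 days = 56 to 60 home readings, plus the visit readings.
- Control arm: 2 readings, at baseline and at 2 weeks.

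**Assumptions.** The documents give no false-pass rate. Let f be the excess share of app-arm continuing smokers, over and above any rate common to both arms, who pass CO and report abstinence. Let c be the share of these who also pass cotinine; c = 1 when CO alone suffices.

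**At the hypothesised quit rates.** Expected app-arm non-quitters = 75 × (1 − 0.20) = 60. Bias in points = 100 × f × c × 60/75.

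| f (assumed) | False quits if CO suffices | Bias, c = 1 | Bias, c = 0.10 | Bias, c = 0 |
|---|---|---|---|---|
| 3% | 1.8 | 2.4 | 0.24 | 0 |
| 5% | 3 | 4 | 0.4 | 0 |
| 10% | 6 | 8 | 0.8 | 0 |

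**If the app does nothing (true rate 10% in both arms, c = 1).** Continuing smokers in the app arm = 75 × 0.90 = 67.5. Spurious difference = 0.90 × f.

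- f = 5%: 3.4 false quits, 4.5 points.
- f = 10%: 6.8 false quits, 9.0 points.
- f = 11.1%: 7.5 false quits, 10.0 points, the whole hypothesised effect.

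The chance of a significant result favouring the app was found by exact enumeration of the pooled z test (two-sided 0.05 assumed, as the plan states no level). It is 2.6% at f = 0, 13% at 5%, 35% at 10% and 41% at 11.1%.

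**Only the excess counts.** With equal true rates, false-pass rates of 10% (app) and 5% (control) give 0.90 × (0.10 − 0.05) = 4.5 points. Equal rates give 0.

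**Against sampling error.** The 95% interval for a 10-point difference has half-width 1.96 × √(0.20 × 0.80/75 + 0.10 × 0.90/75) = 11.3 points. A bias of 4 points could not be seen in the primary result itself. It would have to be looked for in the discordant test results.

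**The case against.** **Controls learn too.** A reader might infer that only the app arm can learn to pass the test. The documents do not support that: controls also see their CO result at each visit and have it explained. The contrast is one of degree, about 60 readings against 2.

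**Two tests may mean both.** Section 4a can be read as requiring both markers, in which case cotinine removes most or all of the bias. That reading is reasonable, but no section states it, and the Carbon Monoxide Breath Test section read alone lets CO indicate abstinence. This limits the claim: the bias reaches the primary endpoint only where CO can verify a quit without a negative cotinine.

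**The motive is weak.** Vouchers depend on attendance, not on results. App users know that their readings reach the study team and are asked how much they smoked, so a false claim would leave a trail. The home and clinic devices also differ (iCO and piCO), and no agreement near 10 ppm is stated. These points make a high false-pass rate less likely. They do not make it equal between arms.

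**The rates are assumed.** This stands. Participants lost to follow-up count as smokers and cannot pass falsely, so 60 is an upper figure for those able to do so.

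**Cotinine has its own weakness.** It is read from a colour chart, and blinding of the tester is stated for baseline only. This is a reason not to make cotinine the sole arbiter.

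**Conclusion.** The concern holds as a possible bias of known direction and unknown size. The shared analyte, the shared cut-off and the very unequal practice are in the text, and nothing in the plan prevents CO alone from verifying a 1-month quit. Under assumed excess false-pass rates of 3% to 10%, the bias is 2.4 to 8 points if CO suffices. It is below 1 point if a negative cotinine is also required and catches 90% of false passers.

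A reader might go further and infer that the primary comparison is biased towards the app. The documents do not establish that. They give no false-pass rate, and they leave open a verification rule under which the effect nearly vanishes. The low cost of settling that rule now is the reason to act.

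**What to change.** In section 7c:

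1. Define verified cessation at 1 month as self-reported abstinence with both CO at or below 10 ppm and a negative urine cotinine. This matches the baseline exclusion, which already needs both tests negative before setting someone aside.
2. Among participants reporting abstinence, tabulate CO-negative/cotinine-positive results by arm. An excess in the app arm would be the direct sign of the problem.
3. Report the primary difference with CO alone and with cotinine alone as sensitivity analyses.

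Letting cotinine decide whenever the tests disagree would be a poorer rule. The primary outcome would then be cotinine alone, a cotinine-only sensitivity analysis would repeat it exactly, and a participant above 10 ppm could count as a quitter.

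**Cost.** A few sentences; both tests are already scheduled at every visit. Some true quitters within about 2 to 4 days of their last cigarette would count as smokers. This lowers both quit rates and slightly shrinks the absolute difference: if an assumed 10% of quitters in each arm are affected, 20% and 10% become 18% and 9%, and the difference falls from 10 to 9 points.

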### **Participant identification and recruitment**

A total of 150 adult smokers will be recruited to participate in this study through several channels, including:

- Patient will be recruited from clinics, inpatient and outpatient facilities within the Johns Hopkins Medical Institutions (JHMI) network in Baltimore. Posters advertising the study will be placed at these clinics and facilities. Recruitment cards with information about the study and contact information for study staff will be provided to physicians and nurses at inpatient and outpatient

Dated: 15 May 2017

facilities to give to their patients and staff. However, inpatients will only be screened for enrollment once they have been discharged.

- JHMI staff will be recruited through the Human Resources office. Posters advertising the study will be placed in the office and recruitment cards will be given to JHMI staff.
- Posters advertising the study will be placed in several locations with high foot traffic around the JHMI East Baltimore campus.
- A Facebook COach2Quit page will be created for recruiting participants online. The page will have information about the study and contact information for study staff. The page will be promoted on a cost per click basis for the duration of the study recruitment period. Audience for the promotion will be limited by the location, interests and age filters provided by Facebook. Location will be limited to Baltimore city, interests will be limited to search terms such as smoking, quitting smoking, tobacco and nicotine, and age will be limited to people over the age of 18 years. **No Personal Health Information (PHI) will be collected online.** Interested participants will be able to contact study staff through the study contact information provided on the Facebook page.
- Center for AIDS Research (CFAR) at Johns Hopkins University: CFAR operates a study hotline, which is a service that pre-screens participants and provides referrals to research studies. CFAR will provide contact information for participants who have identified as smokers and we will contact these participants.

At initial contact with the participant, the study coordinator will discuss the study purpose and requirements and obtain informed consent from interested participants. Whenever possible, the initial assessment will be completed at this time. When this is not practical, the coordinator will schedule an appointment as soon as possible.

